### **9.1.1.1 Replacement policy**

Subjects who discontinue due to reasons other than safety may be replaced.

### **9.1.2 Withdrawal of informed consent**

Subjects may voluntarily withdraw consent to participate in the study for any reason at any time. Withdrawal of consent occurs only when a subject:

- Does not want to participate in the study anymore, **and**
- Does not allow further collection of personal data

In this situation, the investigator should make a reasonable effort (e.g. telephone, e-mail, letter) to understand the primary reason for the subject's decision to withdraw his/her consent and record this information.

Study treatment must be discontinued and no further assessments conducted, and the data that would have been collected at subsequent visits will be considered missing.

Further attempts to contact the subject are not allowed unless safety findings require communicating or follow-up.

All efforts should be made to complete the assessments prior to study withdrawal. A final evaluation at the time of the subject's study withdrawal should be made as detailed in the assessment table.

Novartis will continue to keep and use collected study information (including any data resulting from the analysis of a subject's samples until the time of withdrawal) according to applicable law.

For US: All biological samples not yet analyzed at the time of withdrawal may still be used for further testing/analysis in accordance with the terms of this protocol and of the informed consent form.

For EU and RoW: All biological samples not yet analyzed at the time of withdrawal will no longer be used, unless permitted by applicable law. They will be stored according to applicable legal requirements.

### **9.1.3 Lost to follow-up**

For subjects whose status is unclear because they fail to appear for study visits without stating an intention to discontinue or withdraw, the investigator must show "due diligence" by documenting in the source documents steps taken to contact the subject, e.g. dates of telephone calls, registered letters, etc. A subject should not be considered as lost to follow-up until due diligence has been completed or until the end of the study.

### **9.1.4 Study stopping rules**

Enrollment in the study will be placed on hold if any of the following occurs:

- Two or more similar study-drug related serious adverse events (SAEs)
- The Sponsor considers that the number and/or severity of AEs, abnormal safety monitoring tests or abnormal laboratory findings justify putting the study on hold.

The study may resume following the safety review, if the Lead Investigator(s) and Sponsor agree it is safe to proceed.

### **9.1.5 Early study termination by the sponsor**

The study can be terminated by Novartis at any time for any reason. This may include reasons related to the benefit/ risk assessment of participating in the study, practical reasons (including slow enrollment), or for regulatory or medical reasons. In taking the decision to terminate, Novartis will always consider the subject welfare and safety. Should early termination be necessary, Novartis will contact the investigator with next steps, such as the subjects to be scheduled to be seen as soon as possible and to stop taking study drug, and to be treated as a prematurely withdrawn subject. The investigator may be informed of additional procedures to be followed in order to ensure that adequate consideration is given to the protection of the subject's interests. Depending on local regulations, the investigator or sponsor will be responsible for informing IRBs/IECs of the early termination of the trial.

## **9.2 Study completion and post-study treatment**

Study completion is defined as when the last subject finishes their Study Completion assessments at the End of Study/Early Termination visit and any repeat assessments associated with this visit have been documented and followed-up appropriately by the Investigator or, in the event of an early study termination decision, the date of that decision. Each subject will be required to complete the study in its entirety and thereafter no further study treatment will be made available to them.

All randomized subjects should have a safety follow-up call conducted 30 days after last administration of study treatment, or last study visit, whichever is later. The information collected is kept as source documentation. All SAEs reported during this time period must be reported as described in [Section 10.1.3](#) and SOM). Documentation of attempts to contact the subject should be recorded in the source documentation.

## **10 Safety monitoring and reporting**

### **10.1 Definition of adverse events and reporting requirements**

#### **10.1.1 Adverse events**

An adverse event (AE) is any untoward medical occurrence (e.g. any unfavorable and unintended sign (including abnormal laboratory findings), symptom or disease) in a subject or clinical investigation subject after providing written informed consent for participation in the study. Therefore, an AE may or may not be temporally or causally associated with the use of a medicinal (investigational) product.

The investigator has the responsibility for managing the safety of individual subject and identifying adverse events.

Novartis qualified medical personnel will be readily available to advise on trial related medical questions or problems.

The occurrence of adverse events must be sought by non-directive questioning of the subject at each visit during the study. Adverse events also may be detected when they are volunteered by the subject during or between visits or through physical examination findings, laboratory test findings, or other assessments.

Adverse events must be recorded under the signs, symptoms, or diagnosis associated with them, accompanied by the following information (as far as possible) (if the event is serious refer to [Section 10.1.2](#)):

1. The severity grade:
  - mild: usually transient in nature and generally not interfering with normal activities
  - moderate: sufficiently discomforting to interfere with normal activities
  - severe: prevents normal activities
2. its relationship to the study treatment. If the event is due to lack of efficacy or progression of underlying illness (i.e. progression of the study indication) the assessment of causality will usually be 'Not suspected.' The rationale for this guidance is that the symptoms of a lack of efficacy or progression of underlying illness are not caused by the trial drug, they happen in spite of its administration and/or both lack of efficacy and progression of underlying disease can only be evaluated meaningfully by an analysis of cohorts, not on a single subject
3. its duration (start and end dates) or if the event is ongoing, an outcome of not recovered/not resolved must be reported
4. whether it constitutes a SAE (see [Section 10.1.2](#) for definition of SAE) and which seriousness criteria have been met
5. action taken regarding with study treatment

All adverse events must be treated appropriately. Treatment may include one or more of the following:

- Dose not change
- Drug interrupted/withdrawn

6. its outcome (i.e. recovery status or whether it was fatal)

Conditions that were already present at the time of informed consent should be recorded in medical history of the subject.

Adverse events (including lab abnormalities that constitute AEs) should be described using a diagnosis whenever possible, rather than individual underlying signs and symptoms.

Adverse event monitoring should be continued for at least 30 days following the last dose of study treatment.

Once an adverse event is detected, it must be followed until its resolution or until it is judged to be permanent (e.g. continuing at the end of the study), and assessment must be made at each visit (or more frequently, if necessary) of any changes in severity, the suspected relationship to the interventions required to treat it, and the outcome.

Information about adverse drug reactions for the investigational drug can be found in the Investigator's Brochure (IB).

Abnormal laboratory values or test results constitute adverse events only if they fulfill at least one of the following criteria:

- they induce clinical signs or symptoms
- they are considered clinically significant
- they require therapy

Clinically significant abnormal laboratory values or test results must be identified through a review of values outside of normal ranges/clinically notable ranges, significant changes from baseline or the previous visit, or values which are considered to be non-typical in subjects with the underlying disease. Alert ranges for laboratory and other test abnormalities are referenced in [Appendix 1](#).

Follow the instructions found in the Site Operations Manual for data capture methodology regarding AE collection for subjects that fail screening.

### **10.1.2 Serious adverse events**

An SAE is defined as any adverse event [appearance of (or worsening of any pre-existing)] undesirable sign(s), symptom(s), or medical condition(s) which meets any one of the following criteria:

- fatal
- life-threatening

Life-threatening in the context of a SAE refers to a reaction in which the subject was at risk of death at the time of the reaction; it does not refer to a reaction that hypothetically might have caused death if it were more severe (please refer to the ICH-E2D Guidelines).

- results in persistent or significant disability/incapacity
- constitutes a congenital anomaly/birth defect
- requires inpatient hospitalization or prolongation of existing hospitalization, unless hospitalization is for:
  - routine treatment or monitoring of the studied indication, not associated with any deterioration in COPD.
  - elective or pre-planned treatment for a pre-existing condition that is unrelated to the indication under study and has not worsened since signing the informed consent
  - social reasons and respite care in the absence of any deterioration in the subject's general condition
  - treatment on an emergency outpatient basis for an event not fulfilling any of the definitions of a SAE given above and not resulting in hospital admission
- is medically significant, e.g. defined as an event that jeopardizes the subject or may require medical or surgical intervention to prevent one of the outcomes listed above

Medical and scientific judgment should be exercised in deciding whether other situations should be considered serious reactions, such as important medical events that might not be immediately life threatening or result in death or hospitalization but might jeopardize the subject or might require intervention to prevent one of the other outcomes listed above. Such events should be considered as "medically significant." Examples of such events are intensive treatment in an

emergency room or at home for allergic bronchospasm, blood dyscrasias, or convulsions that do not result in hospitalization or development of dependency or abuse (please refer to the ICH-E2D Guidelines).

All malignant neoplasms will be assessed as serious under “medically significant” if other seriousness criteria are not met

Any suspected transmission via a medicinal product of an infectious agent is also considered a serious adverse reaction.

All reports of intentional misuse and abuse of the product are also considered serious adverse event irrespective if a clinical event has occurred.

### **10.1.3 SAE reporting**

To ensure subject safety, every SAE, regardless of causality, occurring after the subject has provided informed consent and until 30 days after the last study visit must be reported to Novartis safety within 24 hours of learning of its occurrence. Detailed instructions regarding the submission process and requirements are to be found in the investigator folder provided to each site.

**Screen Failures:** If a subject fails screening (e.g. a subject who is screened but is not treated or randomized), SAEs occurring after the subject has provided informed consent until the time the subject is deemed a Screen Failure must be reported to Novartis.

**Randomized Subjects who discontinue prematurely:** SAEs collected between the time a subject signs ICF until 30 days after the subject discontinued or stopped study treatment, or had their last study visit, whichever is later should be reported to Novartis/sponsor safety within 24 hours of learning of its occurrence.

All follow-up information for the SAE including information on complications, progression of the initial SAE and recurrent episodes must be reported as follow-up to the original episode within 24 hours of the investigator receiving the follow-up information. An SAE occurring at a different time interval or otherwise considered completely unrelated to a previously reported one must be reported separately as a new event.

If the SAE is not previously documented in the Investigator's Brochure or Package Insert (new occurrence) and is thought to be related to the study treatment, a Novartis Chief Medical Office and Patient Safety (CMO&PS) Department associate may urgently require further information from the investigator for health authority reporting. Novartis may need to issue an Investigator Notification (IN) to inform all investigators involved in any study with the same study treatment that this SAE has been reported.

Suspected Unexpected Serious Adverse Reactions (SUSARs) will be collected and reported to the competent authorities and relevant ethics committees in accordance with EU Guidance 2011/C 172/01 or as per national regulatory requirements in participating countries.

Any SAEs experienced after the 30 day period after the last study visit should only be reported to Novartis Safety if the investigator suspects a causal relationship to study treatment.

#### 10.1.4 Pregnancy reporting

##### Pregnancies

To ensure subject safety, each pregnancy occurring after signing the informed consent must be reported to Novartis within 24 hours of learning of its occurrence. The pregnancy should be followed up to determine outcome, including spontaneous or voluntary termination, details of the birth, and the presence or absence of any birth defects, congenital abnormalities, or maternal and/or newborn complications.

Pregnancy should be recorded and reported by the investigator to the Novartis Chief Medical Office and Patient Safety (CMO&PS). Pregnancy follow-up should be recorded on the same form and should include an assessment of the possible relationship to the investigational treatment any pregnancy outcome. Any SAE experienced during pregnancy must be reported.

#### 10.1.5 Reporting of study treatment errors including misuse/abuse

Medication errors are unintentional errors in the prescribing, dispensing, administration or monitoring of a medicine while under the control of a healthcare professional, subject or consumer (EMA definition).

Misuse refers to situations where the medicinal product is intentionally and inappropriately used not in accordance with the protocol.

Abuse corresponds to the persistent or sporadic, intentional excessive use of a medicinal product, which is accompanied by harmful physical or psychological effects.

Study treatment errors and uses outside of what is foreseen in the protocol will be recorded on the appropriate CRF irrespective of whether or not associated with an AE/SAE and reported to Safety only if associated with an SAE. Misuse or abuse will be collected and reported in the safety database irrespective of it being associated with an AE/SAE within 24 hours of Investigator's awareness.

**Table 10-1      Guidance for capturing the study treatment errors including misuse/abuse**

Treatment error type	Document in Dosing CRF (Yes/No)	Document in AE eCRF	Complete SAE form
Unintentional study treatment error	Yes	Only if associated with an AE	Only if associated with an SAE
Misuse/Abuse	Yes	Yes	Yes, even if not associated with a SAE

For more information on AE and SAE definition and reporting requirements, please see the respective sections.

## 10.2 Additional Safety Monitoring

### 10.2.1 Liver safety monitoring

To ensure subject safety and enhance reliability in determining the hepatotoxic potential of an investigational drug, a standardized process for identification, monitoring and evaluation of liver events has to be followed.

The following two categories of abnormalities / adverse events have to be considered during the course of the study (irrespective of whether classified/reported as AE/SAE):

- Liver laboratory triggers, which will require repeated assessments of the abnormal laboratory parameter
- Liver events, which will require close observation, follow-up monitoring and contributing factors are recorded on the appropriate CRFs

Please refer to [Table 16-1](#) in Appendix 2 [Section 16.2](#) for complete definitions of liver laboratory triggers and liver events.

Every liver event defined in [Section 16.2](#) should be followed up by the investigator or designated personnel at the trial site, as summarized below. Additional details on actions required in case of liver events and guidance on how to document them are outlined in Section 9 (Appendix 3) of the Site Operations Manual.

- Repeat liver chemistry tests (i.e. ALT, AST, TBL, ALB, PT/INR, ALP and GGT) to confirm elevation. These liver chemistry repeats will be performed using the central laboratory. If results will not be available from the central laboratory, then the repeats can also be performed at a local laboratory to monitor the safety of the subject. If a liver event is subsequently reported, any local liver chemistry tests previously conducted that are associated with this event should have results recorded on the appropriate CRF.
- If the initial elevation is confirmed, close observation of the subject will be initiated, including consideration of treatment interruption\* if deemed appropriate.
- Discontinuation of the investigational drug (refer to the Discontinuation of study treatment [Section 9.1.1](#) and [Table 16-2](#)), if appropriate.
- Hospitalization of the subject if appropriate
- Causality assessment of the liver event
- Thorough follow-up of the liver event should include repeat liver chemistry tests and additional investigation, based on investigator's discretion: serology tests, imaging and pathology assessments, hepatologist's consultancy; obtaining more detailed history of symptoms and prior or concurrent diseases, history of concomitant drug use, exclusion of underlying liver disease.

All follow-up information and procedures performed must be recorded as appropriate in the CRF.

\*Please see [Section 9.1.1](#) for maximum duration of study drug interruption permitted.

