### Commercially Confidential Information

Women of child bearing potential must be informed that taking the study treatment may involve unknown risks to the fetus if pregnancy were to occur during the study and must agree that in order to participate in the study they must adhere to the contraception requirements outlined in the exclusion criteria. If there is any question that the subject will not reliably comply, they should not be entered or continue in the study.

As of January 2018, over 2830 subjects have been exposed to fevipiprant in its clinical development program. Potential side effects of fevipiprant include: increased heart rate, non-serious arrhythmia such as palpitations, headache, diarrhea, nausea, vomiting, nasopharyngitis, somnolence and dizziness.

Cardiovascular risks will be monitored based on changes in vital signs, ECGs and biochemical parameters. Monitoring of liver function tests (LFT) and renal function will be conducted.

In humans, one major metabolite of fevipiprant has been identified which is formed by glucuronidation (acyl glucuronide) and partially binds to plasma proteins. In the literature, in vivo binding of acyl glucuronides to proteins has been reported to be associated with rare idiosyncratic drug reactions (IDRs), although a causal connection of protein adduction to IDRs remains uncertain. There have been no IDRs observed with fevipiprant treatment in completed clinical trials as of January 2018. Surveillance of adverse events for identification of IDRs will be conducted during the course of this study.

Taking fevipiprant at the doses used in this study with the cholesterol-lowering drug simvastatin has been shown to cause a small increase in the peak blood level of simvastatin. Subjects on doses of simvastatin > 20 mg, doses of atorvastatin > 40 mg, doses of pravastatin > 40 mg, or doses of pitavastatin > 2 mg per day, as well as subjects on any statins with high creatine kinase (CK) levels (> 2 X ULN (upper limit of normal)) at screening will be excluded from the study. Subjects on statin medication who are included in the study will have regular monitoring for relevant symptoms and be subject to discontinuation based on persistent myalgia and/or blood CK levels.

Kindly refer to the Investigator's Brochure for further guidance on the risk-benefit assessment of fevipiprant.

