### **6.6.3 Emergency breaking of assigned treatment code**

Emergency code breaks must only be undertaken when it is required to in order to treat the subject safely. Most often, study treatment discontinuation and knowledge of the possible treatment assignments are sufficient to treat a study subject who presents with an emergency condition. Emergency treatment code breaks are performed using the IRT. When the investigator contacts the system to break a treatment code for a subject, he/she must provide the requested subject identifying information and confirm the necessity to break the treatment code for the subject. The investigator will then receive details of the investigational drug treatment for the specified subject and a fax or email confirming this information. The system will automatically inform the monitor for the site and the study team that the code has been broken.

It is the investigator's responsibility to ensure that there is a dependable procedure in place to allow access to the IRT at any time in case of emergency. The investigator will provide:

- protocol number
- subject number

In addition, oral and written information must be provided to the subject on how to contact the investigator in cases of emergency, or when he/she is unavailable, to ensure that un-blinding can be performed at any time.

If a subject has their treatment code revealed they should discontinue study treatment. They should continue to be followed up in the study, as outlined in [Section 9.1.1](#).

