## **9 Study discontinuation and completion**

### **9.1 Discontinuation**

#### **9.1.1 Discontinuation of study treatment**

Discontinuation of study treatment for a subject occurs when study treatment is stopped earlier than the protocol planned duration. Discontinuation of study treatment can be decided by either the subject or the investigator.

Study treatment must be discontinued under the following circumstances:

- Subject decision - subjects may choose to discontinue study treatment for any reason at any time.
- The investigator believes that continuation would negatively impact the safety of the subject, the integrity of the trial or the risk/benefit ratio of trial participation.
- An adverse event graded as 'severe' or "serious" if it is considered related to study treatment.
- Any protocol deviation that results in a significant risk to the subject's safety.
- Pregnancy (see [Section 8.4.3](#) and [Section 10.1.4](#)).
- Female subjects non-compliant with the chosen effective method of contraception during the study: The investigator must provide appropriate advice on the continued use of

effective contraception for at least one week (at least 5 half-lives of QAW039) after study drug discontinuation.

- Use of prohibited treatment as outlined in [Table 6-2](#).
- COPD exacerbation requiring use of systemic steroids and/or antibiotics.
- Total white blood cell count <1000 cells/ $\mu$ L of blood.
- If a liver or renal event occurs, follow guidelines outlined in [Section 16.2](#) and [Section 16.3](#) regarding confirmation of safety monitoring signal and discontinuation of study treatment.
- If patients on statin therapy complain of persistent muscle pain without any obvious cause for greater than 3 days accompanied by increase in CK levels > 10xULN or persistent intolerable muscle pain regardless of the accompanying CK level.
- Moderate or severe hypersensitivity reaction occurs, including any of the following: anaphylaxis, fever, chills, urticaria, dyspnea, headache, myalgia, hypotension.
- Any laboratory abnormalities that in the judgment of the investigator, taking into consideration the subject's overall status, prevents the subject from continuing participation in the study.
- The following deviations from the prescribed dose regimen for the study drug:
  1. More than 10 missed doses
  2. More than 7 consecutive missed doses

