- The appropriate personnel from the site and Novartis will assess whether investigational drug treatment should be discontinued for any subject whose treatment code has been broken inadvertently for any reason.

If discontinuation of study treatment occurs, the Investigator must determine the primary reason for the subject's premature discontinuation of study treatment and record this information on the Dosage Administration CRF.

Subjects who discontinue study treatment or who decide they do not wish to participate in the study further should NOT be considered withdrawn from the study UNLESS they withdraw their consent (see [Section 9.1.2](#), Withdraw of Informed Consent).

Subjects who prematurely discontinue from the study will be encouraged to return for scheduled study visits, depending on the cause for discontinuation (either scheduled as soon as possible and/or for the Early Termination visit approximately 28 days after their last treatment). The Investigator should contact Novartis for guidance. If they fail to return for these assessments for unknown reasons, every effort (e.g. telephone, e-mail, letter) should be made to contact the subject/pre-designated contact as specified in [Section 9.1.3](#) (Lost to follow-up). This contact should preferably be done according to the study visit schedule.

After study treatment discontinuation, at a minimum, in abbreviated visits, the following data should be collected at clinic visits or via telephone/email contact:

- new / concomitant treatments
- adverse events/Serious Adverse Events

The investigator/deputy must also contact the IRT to register the subject's discontinuation from study treatment.

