**Table 16-2 Follow up requirements for liver events and laboratory triggers**

Criteria	Actions required	Follow-up monitoring
Potential Hy's Law case a	
 
Discontinue the study treatment immediately
 
Hospitalize, if clinically appropriate
 
Establish causality
 
Record the AE and contributing factors (e.g. conmeds, med hx, lab) in the appropriate CRF
 
	ALT, AST, TBL, Alb, PT/INR, ALP and GGT until resolution b (frequency at investigator discretion)
ALT or AST		
$\geq 3 \times \text{ULN}$	
 
Discontinue the study treatment immediately
 
Hospitalize if clinically appropriate
 
Establish causality
 
Record the AE and contributing factors (e.g. conmeds, medical history, lab) in the appropriate CRF
 
	ALT, AST, TBL, Alb, PT/INR, ALP and GGT until resolution b (frequency at investigator discretion)
$\geq 2.5 \times \text{ULN}$ and total bilirubin $\geq 1.5 \times \text{ULN}$	
 
Discontinue the study drug and continue follow-up monitoring
 
Establish causality
 
Record the AE and contributing factors (e.g. conmeds, medical history, lab) in the appropriate CRF
 
	ALT, AST, TBL, Alb, PT/INR, ALP and GGT until resolution b (frequency at investigator discretion)
ALP (isolated)		
$> 2 \times \text{ULN}$ (in the absence of known bone pathology)	
 
Repeat LFT within 48 hours
 
If elevation persists, establish causality
 
Record the AE and contributing factors (e.g. conmeds, med hx, lab) in the appropriate CRF
 
	Investigator discretion Monitor LFT within 1 to 4 weeks or at next visit
TBL (isolated)		
$> 2 \times \text{ULN}$ (in the absence of known Gilbert syndrome)	
 
Repeat LFT within 48 hours
 
If elevation persists, discontinue the study drug immediately
 
Hospitalize if clinically appropriate
 
	ALT, AST, TBL, Alb, PT/INR, ALP and GGT until resolution b (frequency at investigator discretion) Test for hemolysis (e.g. reticulocytes, haptoglobin, unconjugated [indirect] bilirubin)

Criteria	Actions required	Follow-up monitoring

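### Protocol stopping instructions conflict in two places: certain liver events (Section 10.2.1 against Table 16-2) and inadvertent code breaks (Section 6.6.3 against Section 9.1.1)

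*Protocol*

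**What the plan says.** **Liver.** Protocol Section 10.2.1 applies its follow-up list to every liver event defined in Section 16.2. The list opens with "Repeat liver chemistry tests (i.e. ALT, AST, TBL, ALB, PT/INR, ALP and GGT) to confirm elevation". The next item reads "If the initial elevation is confirmed, close observation of the subject will be initiated, including consideration of treatment interruption", and that sentence ends by leaving interruption to what is deemed appropriate. The third item is "Discontinuation of the investigational drug (refer to the Discontinuation of study treatment", with a pointer to Section 9.1.1 and Table 16-2, and it too applies only where appropriate.

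Table 16-2 gives actions row by row. For a potential Hy's Law case and for ALT or AST at or above 3 x ULN, the first action is "Discontinue the study treatment immediately". For ALT or AST at or above 2.5 x ULN with total bilirubin at or above 1.5 x ULN, the study drug is also discontinued. For isolated total bilirubin above 2 x ULN, the test is repeated within 48 hours and the drug is stopped if the elevation persists. Section 9.1.1 sends liver and renal events to Sections 16.2 and 16.3.

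**Code break.** Section 6.6.3 states: "If a subject has their treatment code revealed they should discontinue study treatment". Section 9.1.1 states that site and sponsor personnel "will assess whether investigational drug treatment should be discontinued for any subject whose treatment code has been broken inadvertently for any reason". That item sits in a list introduced as circumstances in which treatment must be stopped.

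**The concern.** A stopping rule has to give the same answer wherever an investigator looks it up, and Section 10.2.1 itself sets out to provide a standardized process for liver events. Here, an investigator who opens Section 10.2.1 after a first ALT of 3 x ULN or more is told to repeat the test and then to consider interruption. One who opens Table 16-2 is told to stop at once. After an accidental unblinding, Section 6.6.3 points to stopping and Section 9.1.1 to an assessment that may end in continued treatment.

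What is at stake is subject safety and uniform conduct across sites: the same event could be handled in opposite ways, with each site able to cite the protocol.

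**Working it through.** The documents give no figure to reproduce and no arithmetic applies. The check sets the instructions side by side, event by event. The liver-event definitions are in Table 16-1.

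| Event | Section 10.2.1 | Table 16-2 | Result |
|---|---|---|---|
| Potential Hy's Law case | Repeat; if confirmed, observe and consider interruption | Stop immediately; no repeat step | Conflict |
| ALT or AST at or above 3 x ULN | Same | Stop immediately; no repeat step | Conflict |
| ALT or AST at or above 2.5 x ULN with bilirubin at or above 1.5 x ULN | Same | Stop; no repeat step | Conflict |
| Isolated bilirubin above 2 x ULN | Same | Repeat; stop if it persists | Agree on the repeat; differ after confirmation |
| Isolated ALP above 2 x ULN | Same | Repeat; stopping not required | No material conflict |
| Adverse event suggestive of liver toxicity | Same | Interruption or discontinuation to be considered | No material conflict |

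Can the cross-references resolve the first four rows? Section 10.2.1 names Table 16-2 in its discontinuation item, and Section 9.1.1 leads to the same place through Section 16.2. But the item in Section 10.2.1 is conditional on discontinuation being appropriate, whereas these rows of the table leave no such discretion. Section 9.1.1 also refers to confirming the safety signal, a step that the ALT/AST and Hy's Law rows do not contain. The cross-references soften the conflict without removing it.

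**Code break, by cause:**

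- Emergency break: Section 6.6.3 says the subject should stop. Section 9.1.1 has no separate item for it, so there is no direct conflict.
- Inadvertent break: the sentence in Section 6.6.3 is not limited by cause, so as worded the subject should stop. Section 9.1.1 calls for an assessment, so the two conflict.
- Within Section 9.1.1 itself, a case-by-case item stands in a mandatory list.

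**The case against.** **Liver.** The list in Section 10.2.1 is unnumbered, is presented as a summary, and includes hospitalization and causality assessment. It can be read as a menu of actions, not a sequence. Repeating tests and stopping drug can happen together, and the ALT/AST rows of Table 16-2 call for follow-up with the same panel. Both routes for discontinuation end at Table 16-2, so the condition could mean: where that table requires it. The confirmation wording in Section 9.1.1 covers renal as well as liver events, and confirmation steps do exist elsewhere in Sections 16.2 and 16.3. Section 10.2.1 also refers to the Site Operations Manual for further actions, and that manual is not among the documents.

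Much of this stands. It shows that a careful reader could reach one answer, but not that the text gives one. Considering interruption after confirmation is a different instruction from stopping immediately.

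**Code break.** Section 6.6.3 is headed as emergency code breaking, so the two rules might be divided by scope. Neither passage states that division.

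**Statin users and CK.** A reader might infer a third conflict. Section 4.5 says that statin users will "be subject to discontinuation based on persistent myalgia and/or blood CK levels", which could admit CK alone. The specific rule in Section 9.1.1 requires either persistent muscle pain with CK above 10 x ULN or "persistent intolerable muscle pain regardless of the accompanying CK level". The documents do not support calling this a contradiction. Section 4.5 is a risk summary with no threshold, Section 9.1.1 holds the operative rule, and its general item on laboratory abnormalities already lets the investigator stop treatment on a laboratory value. It is loose wording.

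**Conclusion.** The point holds for two pairs of passages: Section 10.2.1 against Table 16-2 for the three ALT/AST-based liver events, and in part for persistent isolated bilirubin above 2 x ULN; and Section 6.6.3 against Section 9.1.1 for inadvertent code breaks. It does not extend to isolated ALP or to adverse events suggestive of liver toxicity. That sites would act differently is a plausible consequence, not something the documents state. It assumes that the Site Operations Manual does not already settle the matter.

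The size cannot be stated, because no frequency is given for any of these events. Two further inferences are tempting but not supported:

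- **Extra doses.** A reader might use the repeat intervals in Table 16-2 to count additional daily doses under a repeat-first reading. Section 10.2.1 gives no interval. The 48 hours belongs to the isolated ALP and bilirubin rows. The one-week interval belongs to bilirubin above 1.5 and up to 2 x ULN, which Table 16-1 classes as a laboratory trigger, so the liver-event list does not cover it.
- **Effect on the primary analysis.** Section 12.4.3 restricts the model to trial completers, so a reader might infer that inconsistent stopping alters the primary data. But under Section 9.1.1 stopping treatment is not withdrawal from the study, and subjects are encouraged to return for visits. Section 12.8.1 continues randomization until about 50 subjects complete the end-of-treatment visit. The estimand and model details are redacted, so how week 6 data from subjects off treatment would be handled cannot be seen.

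**What to change.** Reconcile the following, so that each event carries a single instruction in both places:

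1. Section 10.2.1 with Table 16-2, for the Hy's Law, ALT/AST and isolated bilirubin rows, including whether a confirmation step applies.
2. Section 6.6.3 with the code-break item in Section 9.1.1. State whether emergency and inadvertent breaks are treated alike, and word the item so that it fits the list in which it stands.

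As a minor edit, align the statin and CK sentence in Section 4.5 with the rule in Section 9.1.1.

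Which instruction is right in each pair is a clinical decision for the sponsor, and none is proposed here. The cost is wording in an amendment, with no change to visits, samples or subject numbers.
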